3.1 Safety Analysis Sets

Safety Set

All subjects who

- have signed an informed consent form, undergone screening procedure(s) and received a subject number,
- received a study vaccination,
- provided post vaccination safety data.

Safety per protocol set

All subjects in the safety Set with the exclusions of the following cases:

- (1) Subjects administered prior to the contract date.
- (2) Subjects who didn't receive MenACWY-CRM.
- (3) Subjects who already receive MenACWY-CRM.
- (4) Follow-up failure: The subjects whose safety information cannot be identified due to follow-up loss.
- (5) Not applicable to the indication of study drug
[Indication]
 - To prevent invasive meningococcal disease caused by Neisseria meningitidis serogroups A, C, Y and W-135 in persons 2 through 55 years of age.
- (6) Subjects who violate of Protocol: Those who do not meet one item at least of the inclusion/exclusion criteria.
[Inclusion criteria]
 - 1) Male and female subjects from 2 to 55 years of the age at the time of Visit 1 (including all 55 years old subjects, up to one day before their 56th year birthday), who are scheduled to receive vaccination with MenACWY-CRM conjugate vaccine, according to the local prescribing information and routine clinical practice.
 - 2) To whom the nature of the study has been described and the subject or subject's parent/legal representative has provided written informed consent.
 - 3) Whom the investigator believes that the subject can and will comply with the requirements of the protocol.

	CONFIDENTIAL :	Last Update Date
	THIS DOCUMENT AND INFORMATION CONTAINED HEREIN IS PROPRIETARY TO COMPANY AND IS NOT TO BE DISCLOSED WITHOUT THE WRITTEN PERMISSION OF COMPANY.	22-NOV-2013
STATISTICAL ANALYSIS PLAN(V2.0)		

- 4) Who are in good health as determined by the outcome of medical history, physical assessment and clinical judgment of the investigator.
[Exclusion criteria]
- 1) Contraindication, special warnings and/or precautions, as evaluated by the investigators, reported in the MenACWY-CRM conjugate vaccine Korean prescribing information
- (7) Subjects who prescribed off-label dosage.
 - Violation of intramuscular injection only (0.5ml)

Non-Safety per protocol set

Subjects excluded from safety per protocol set except for subjects who did not receive MenACWY-CRM and follow-up failure.

Based on rules for estimation of each number of safety evaluation cases, the following local regulation and Guideline on Standards for re-examination for new drugs, etc ※ of MFDS, non-safety analysis set are excluded from the safety analysis set:

※ Guideline on Standards for re-examination for new drugs, etc (Chapter II, no. 3)

Patient Population for Surveillance

- A) Patients planned to receive a drug under surveillance by investigator's medical judgment shall be subject.
- B) Subject who do not use within approved range shall not be included in the subject in principal.
 - ※ However, if data of subject whose use is beyond approved range is collected, perform analysis as a separate item.
- C) Describe actual selection methods of subject in detail.

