3.1 Safety Analysis Sets

Safety Set

All subjects who

- have signed an informed consent form, undergone screening procedure(s) and received a subject number,
- received a study vaccination,
- provided post vaccination safety data.

Safety per protocol set

All subjects in the safety Set with the exclusions of the following cases:

- (1) Subjects administered prior to the contract date.
- (2) Subjects who didn't receive MenACWY-CRM.
- (3) Follow-up failure: The subjects whose safety information cannot be identified due to follow-up loss.
- (4) Not applicable to the indication of study drug
[Indication]
- To prevent invasive meningococcal disease caused by Neisseria meningitides serogroups A, C, Y and W-135 in persons 2 months through 55 years of age.
- (5) Subjects who violate of Protocol: Those who do not meet one item at least of the inclusion/exclusion criteria.
[Inclusion criteria]
 - 1) Male and female subjects from 2 months to 55 years of the age at the time of Visit 1 (including all 55 years old subjects, up to one day before their 56th year birthday), who are scheduled to receive vaccination with MenACWY-CRM conjugate vaccine, according to the local prescribing information and routine clinical practice.
 - 2) To whom the nature of the study has been described and the subject or subject's parent/legal representative has provided written informed consent.
 - 3) Whom the investigator believes that the subject can and will comply with the requirements of the protocol.
 - 4) Who are in good health as determined by the outcome of medical history, physical

	CONFIDENTIAL :	Last Update Date
	THIS DOCUMENT AND INFORMATION CONTAINED HEREIN IS PROPRIETARY TO COMPANY AND IS NOT TO BE DISCLOSED WITHOUT THE WRITTEN PERMISSION OF COMPANY.	20-APR-2018
STATISTICAL ANALYSIS PLAN(V6.0)		

assessment and clinical judgment of the investigator.

[Exclusion criteria]

- 1) Contraindication, special warnings and/or precautions, as evaluated by the investigators, reported in the MenACWY-CRM conjugate vaccine Korean prescribing information
 - 2) Infants who were already enrolled in this trial for previous vaccination.
- (6) Subjects who prescribed off-label dosage:
- Vaccine schedule for children from 2 to 23 months of age :

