6.2.3 Analysis of Unsolicited AE

All unsolicited AEs and MAAE recorded in the CRF will be mapped to preferred terms using the most recent MedDRA dictionary and classified by System organ class (SOC) and Preferred Terms (PT). Under the classification standard of MedDRA terms, and all AEs excluding the AEs whose causal relation with the study medication is ‘Not Related’ shall be treated as AEs whose causal relation cannot be excluded {hereafter “Adverse Drug Reaction(ADR)”}.

- ① The frequency and percentage of unsolicited AE (Day 1-7) and MAAE (Day 1-29) according to the expected, serious, severity, frequency, action taken, outcome, relationship to MenACWY-CRM regarding occurred AE will be calculated.
- ② The frequency of unsolicited AEs (Day 1-7) and MAAE (Day 1-29) will be classified into the preferred terms according to the expected, serious, severity, frequency, action taken, outcome, relationship to MenACWY-CRM.
- ③ The number of subjects and percentage of SAE/Serious ADR (SADR), unexpected AE/ADR,

	CONFIDENTIAL :	Last Update Date
	THIS DOCUMENT AND INFORMATION CONTAINED HEREIN IS PROPRIETARY TO COMPANY AND IS NOT TO BE DISCLOSED WITHOUT THE WRITTEN PERMISSION OF COMPANY.	20-APR-2018
STATISTICAL ANALYSIS PLAN(V6.0)		

MAAE/ADR, unsolicited AE/ADR and continuous solicited AE/ADR will be calculated according to the preferred terms. And the number of subjects and percentage by study vaccination number of SAE/Serious ADR (SADR), unexpected AE/ADR, MAAE/ADR, unsolicited AE/ADR and continuous solicited AE/ADR will be calculated according to the preferred terms in infants 2 to 23 months.

- ④ For subjects excluded from safety per protocol set[†], the number of subjects and the percentage of SAE/Serious ADR (SADR), unexpected AE/ADR, MAAE/ADR, unsolicited AE/ADR and continuous solicited AE/ADR will be calculated according to the preferred terms. And the number of subjects and percentage by study vaccination number of SAE/Serious ADR (SADR), unexpected AE/ADR, MAAE/ADR, unsolicited AE/ADR and continuous solicited AE/ADR will be calculated according to the preferred terms in infants 2 to 23 months.

[†] Subject excluded from safety per protocol set: Except for subjects who didn't receive study vaccination and follow-up failure.

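### The set meant to isolate use outside the approved range also holds exclusions that can be on-label, and no planned table separates the two

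*SAP*

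**What the plan says.** SAP V6.0, section 3.1, takes the Safety Set and removes six kinds of subject to form the Safety per protocol set. Four of the six matter here:

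- item 1: "Subjects administered prior to the contract date"
- item 4: "Not applicable to the indication of study drug"
- item 5: "Subjects who violate of Protocol: Those who do not meet one item at least of the inclusion/exclusion criteria"
- item 6: "Subjects who prescribed off-label dosage", with the infant and the 2-to-55-year schedules listed beneath it

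Items 2 and 3 are non-recipients and follow-up failures. The Non-Safety per protocol set is then defined as "Subjects excluded from safety per protocol set except for subjects who did not receive MenACWY-CRM and follow-up failure".

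The same section reproduces a guideline excerpt saying that subjects who use the product outside its approved range should in principle not be included. It adds: "However, if data of subject whose use is beyond approved range is collected, perform analysis as a separate item".

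For the excluded subjects, section 6.2.3 item 4 plans "the number of subjects and the percentage of SAE/Serious ADR (SADR), unexpected AE/ADR, MAAE/ADR, unsolicited AE/ADR and continuous solicited AE/ADR" by preferred term, with a further breakdown by study vaccination number in infants. Section 7.3 repeats that list. The definition of the set and the guideline excerpt read the same in V2.0 as in V6.0.

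**The concern.** The cited rule is about use beyond the approved range. The set that answers it is built from failure to enter the per-protocol set, which is a wider category. Someone vaccinated within label, but before the site's contract date or despite doubtful expected compliance, sits in the same denominator as someone given an off-label dosage or schedule.

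A reader of the re-examination report who wants to know what happened after off-label use would see one mixed percentage, with no count of how many subjects behind it were off-label. Day 1-7 solicited reactions are the first of the four endpoints in section 4.1, and they are not in the list of analyses for this set.

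**Working it through.** There is no figure in the plan to reproduce. The check is of set membership and of which tables each set receives.

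**1. Who is in the set (V6.0, section 3.1).** Exclusion items {1, 2, 3, 4, 5, 6}, less non-recipients (2) and follow-up failures (3), leave {1, 4, 5, 6}.

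| Item | Content | Relation to the approved range |
|---|---|---|
| 1 | Vaccinated before contract date | Can be fully on-label |
| 4 | Outside indication (age) | Outside |
| 5 | Any inclusion or exclusion criterion failed | Mixed: good health, expected compliance and repeat infant enrolment can be on-label; age and label contraindications may not be |
| 6 | Off-label dosage or schedule | Outside |

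Items 4 and 5 overlap. A subject over the age limit is outside the indication and also fails inclusion criterion 1, so any split needs a precedence rule.

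**2. Is the set broken down by reason?** The planned breakdowns are by preferred term, by age and, in infants, by study vaccination number. None is by exclusion item. Section 7.1 asks only for contracted subjects, retrieved case report forms and the safety population.

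**3. What do the age bands recover?** The V4.0 shells give a column for age 56 and over in Non-Safety Tables 8.3.1, 9.3.1, 10.3.1 and 11.3.1, and rows or columns for it in the Safety Set solicited tables (3.1.5, 4.1.3, 4.1.6, 4.1.9, 4.1.10). So over-age use is visible. In V6.0 the bands in section 6.2.1 are 35-55 and 55-64, which overlap at 55, although 55-year-olds are eligible until the day before their 56th birthday. Section 6.3 uses 19-64, which mixes in-range and out-of-range ages. No age band identifies item 6, and the infant split by vaccination number does not show whether a dose departed from the schedule.

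**4. Solicited events, Day 1-7.** Sections 3 and 4 of the V4.0 shells exist for the Safety Set and the Safety per protocol set only. For the Non-Safety set, the only solicited item is continuous solicited events (Table 11.3.1), a term the SAP does not define. Sections 6.2.3 item 4 and 7.3 of V6.0 agree with this. The V5.0 and V6.0 shells are not in the supplied text, so for V6.0 the finding rests on those two sections.

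**5. Why the denominator matters (illustration only).** With zero events among n subjects, the exact two-sided 95% upper limit is 1 − 0.025^(1/n).

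- n = 100: 3.6%
- n = 50: 7.1%
- n = 20: 16.8%
- n = 10: 30.8%

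If a pooled set of 100 had no serious events and 10 to 50 of its members were off-label, the data would rule out only rates above 30.8% to 7.1% for off-label use, not above 3.6%. The set sizes here are assumed, and the SAP plans no confidence interval for this set. The illustration shows why a separate count is needed; it does not estimate any bias.

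**The case against.** The strongest reply is that a separate analysis does exist. Excluded subjects have their own results for serious, unexpected, medically attended, unsolicited and continuous solicited events. The excerpt in section 3.1 asks only for a separate item; it names no table, no event class and no split by reason, and the full guideline is not available here. This stands. A reader might infer that the separate analysis is missing altogether, or that the plan breaches the rule it cites. The documents support neither. The solicited gap is measured against the SAP's own endpoint list, not against the guideline.

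Two other strong readings also fail. Off-label reactogenicity is not wholly hidden, because over-age subjects have their own solicited rows in the V4.0 Safety Set tables. Nor does removing on-label subjects contaminate the per-protocol set: it makes that set smaller but puts no off-label use into it.

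Pooled solicited counts for the excluded group could be obtained by subtracting the per-protocol tables from the Safety Set tables. That is broadly right, but the result is the same mixture.

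The on-label share may also be small. Enrolment runs from the contract date, so item 1 should be rare, and the Safety Set already requires signed consent. That is plausible, and counts by item would settle it.

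Finally, part of item 5 is contraindicated use, which cannot readily be carved out. Protocol Amendment 1 collapses the contraindications, warnings and precautions into a single coded exclusion criterion. This stands and limits the fix.

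**Conclusion.** The point holds in a limited form. The Non-Safety per protocol set is the plan's vehicle for use beyond the approved range, but it pools items 4 and 6 with item 1 and all of item 5. Off-label dosage or schedule use cannot be distinguished from other exclusions in any planned table. No general Day 1-7 solicited summary is listed for the set, and no counts by reason are planned.

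No quantitative bias is claimed: neither the size of the set nor its off-label share is given. The conclusion assumes that the V6.0 shells, which are not supplied, follow the V6.0 text and the V4.0 layout. It is a fault of labelling and tabulation in a descriptive study, worth correcting because the correction is cheap and makes the tables match the rule the SAP quotes.

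**What to change.** - In section 3.1, split the Non-Safety per protocol set into (a) items 4 and 6, and (b) items 1 and 5 only. Anyone who meets item 4 or 6 goes to (a), even if item 1 or 5 also applies.
- Show item 5 as its own row within (b). Do not try to divide it into contraindicated use and the rest, since one exclusion code covers both.
- Run the section 6.2.3 item 4 tables for (a) and (b) separately.
- Add a Day 1-7 solicited-event summary for (a), for under 6 years and 6 years and over, using the existing severity definitions.
- In section 7.1, report the number of subjects excluded under each item.

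The exclusion item must already be assigned to build the per-protocol set, so no new data are needed. The cost is revised wording, a few extra tables and some small cells.

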3.2 Efficacy Analysis Set

Not Applicable

	CONFIDENTIAL :	Last Update Date
	THIS DOCUMENT AND INFORMATION CONTAINED HEREIN IS PROPRIETARY TO COMPANY AND IS NOT TO BE DISCLOSED WITHOUT THE WRITTEN PERMISSION OF COMPANY.	22-NOV-2013
STATISTICAL ANALYSIS PLAN(V2.0)		

4. Endpoints

4.1 Safety Endpoints

Safety will be assessed after administration of study vaccine in terms of the number and percentage of subjects with:

- Local and systemic solicited adverse events reported from study Day 1 (day of vaccination) through study Day 7 post-vaccination;
- Unsolicited AEs reported from study Day 1 (day of vaccination) through study Day 7 post-vaccination;
- Medically attended AEs reported from study Day 1 to study termination (Day 29/early termination);
- SAEs reported from study Day 1 to study termination (Day 29/early termination).

5. Assessment Criteria

5.1 Safety Assessment Criteria

Not Applicable

6. Statistical Analyses

6.1 Baseline Characteristics

Descriptive statistics (mean, standard deviation, median, minimum and maximum) for baseline characteristics such as age, height and weight at enrollment will be calculated in the Safety set and Safety per Protocol set.

The following baseline characteristics will be reported:

	CONFIDENTIAL :	Last Update Date
	THIS DOCUMENT AND INFORMATION CONTAINED HEREIN IS PROPRIETARY TO COMPANY AND IS NOT TO BE DISCLOSED WITHOUT THE WRITTEN PERMISSION OF COMPANY.	22-NOV-2013
STATISTICAL ANALYSIS PLAN(V2.0)		

< Subject Baseline Information >

- gender, age, ethnic origin, weight, height, past diagnosis, pre-Immunization temperature, temperature location, pregnancy

< Study Vaccine Information >

- vaccine site, concomitant medications

6.2 Safety Analyses

The number of subjects of AE[†] and the number of AEs[†] incurred shall be calculated, the incidence rate of AEs[†] and its 95% confidence interval will be calculated using the normal approximation on the safety set and safety per protocol set.

† AE : AE includes solicited and unsolicited AE (DAY 1-7), medically attended AE (DAY 1-29) and SAE (DAY 1-29).

6.2.1 Adverse Events by Baseline Characteristics

AE[†]s (as described below) will be reported (n, %) for the following the baseline characteristics in the safety set and safety per protocol set :

- Age group (2-10, 11-18, 19-34, 35-55)
- Children group (<18, ≥18)
- Gender (male, female)
- Past diagnosis (yes, no)
- Temperature location (axillary, oral, rectal, ear)
- Administration site (left deltoid, right deltoid, other)
- Concomitant medication (yes, no)
- Kidney disorder (yes, no)
- Liver disorder (yes, no)
- Pregnancy (yes, no)

The n(%) of AEs[†] and its 95% confidence interval will be calculated using the normal approximation and analyzed using χ^2 - test or Fisher's exact test.

	CONFIDENTIAL :	Last Update Date
	THIS DOCUMENT AND INFORMATION CONTAINED HEREIN IS PROPRIETARY TO COMPANY AND IS NOT TO BE DISCLOSED WITHOUT THE WRITTEN PERMISSION OF COMPANY.	22-NOV-2013
STATISTICAL ANALYSIS PLAN(V2.0)		

† AE : AE includes solicited and unsolicited AE (DAY 1-7) and medically attended AE (DAY 1-29) and SAEs.

6.2.2. Analysis of Solicited AE

Frequencies and percentages of subjects experiencing each adverse event will be presented for each symptom severity. Summary tables showing the occurrence of any local or systemic adverse events overall and at each time point will also be presented (see Table 4.1.3 and 4.2.3).

Post-vaccination adverse events reported from Day 1 to Day 7 will be summarized by maximal severity. The severity of local adverse events for subjects < 6 years of age will be categorized as follows. Injection-site erythema and induration : absent (0 to 9 mm), mild (10 to 25 mm), moderate (26 to 50 mm), severe (>50 mm); injection-site tenderness: none, mild (minor light reaction to touch), moderate (cried or protested to touch), severe (cried when injected limb was moved). For subjects ≥ 6 years, injection-site erythema and induration absent (1 to 24 mm), mild (25 to 50 mm), moderate (51 to 100 mm), severe (>100 mm); pain: none, mild (present but does not interfere with activity), moderate (interferes with activity), severe (prevents daily activity).

For subjects ≥ 6 years of age, the severity of systemic adverse events (i.e., chills, nausea, malaise, generalized myalgia, generalized arthralgia, headache) occurring up to 7 days after each vaccination will be categorized as none, mild (present but not interfering with daily activity), moderate (some interference with daily activity), and severe (prevents daily activity) except for rash, which will be categorized as none, urticarial, or other.

For subjects < 6 years of age, the severity of systemic adverse events occurring up to 7 days after each vaccination will be categorized as follows. Change in eating habits : none (no change in appetite), mild (eating less than normal for 1 to feeds), moderate (missed 1 or 2 feeds), severe (missed more than 2 feeds); sleepiness : none (no change in alertness), mild (shows an increased alertness), moderate (sleeps through feeds), severe (sleeps most of the time and it is hard to arouse him/her); irritability : none (no change in child disposition), mild (requires more cudding and he/she is less playful than usual), moderate (more difficult to settle), severe (unable to console); rash : none, urticarial, or other; vomiting : none, mild (1-2 episodes/24 hours), moderate (>2 episodes/24 hours), severe (requires outpatient hydration); diarrhea : none (fewer than 2 loose stools/24 hours), mild (2-3 loose stools or < 400 gms/24 hours), moderate (4-5 stools or 400-800 gms/24 hours), severe (6 or more watery stools

	CONFIDENTIAL :	Last Update Date
	THIS DOCUMENT AND INFORMATION CONTAINED HEREIN IS PROPRIETARY TO COMPANY AND IS NOT TO BE DISCLOSED WITHOUT THE WRITTEN PERMISSION OF COMPANY.	22-NOV-2013
STATISTICAL ANALYSIS PLAN(V2.0)		

or > 800 gms/24 hours or requires outpatient IV hydration).

Body temperature will be categorized as <38°C (no fever), ≥38°C (fever) and will be summarized by 0.5°C increments from 36.0°C up to ≥40°C. Additionally, no fever vs. fever will be reported.

Each local and systemic adverse event will also be categorized as none vs. any.

6.2.3 Analysis of Unsolicited AE

All unsolicited AEs and MAAE recorded in the CRF will be mapped to preferred terms using the most recent MedDRA dictionary and classified by System organ class (SOC) and Preferred Terms (PT). Under the classification standard of MedDRA terms, and all AEs excluding the AEs whose causal relation with the study medication is ‘Not Related’ shall be treated as AEs whose causal relation cannot be excluded {hereafter “Adverse Drug Reaction(ADR)”}.

- ① The number and percentage of unsolicited AE (Day 1-7) and MAAE (Day 1-29) and SAEs (Day 1-29) according to the serious, severity, frequency, action taken, outcome, relationship to MenACWY-CRM regarding occurred AE will be calculated.
- ② Unsolicited AEs (Day 1-7) and MAAE (Day 1-29) and SAEs (Day 1-29) will be classified into the preferred terms according to the serious, severity, frequency, action taken, outcome, relationship to MenACWY-CRM. Also, the number and percentage of each AE (PT) will be calculated.
- ③ The number of subjects and the number of unexpected AE/ADR, SAE/Serious ADR (SADR) and MAAE/ADR will be calculated according to the preferred terms. Also, the incidence rate will be estimated.
- ④ For subjects excluded from safety per protocol set[†], the number of subjects and the number of unexpected AE/ADR, SAE/Serious ADR (SADR) and MAAE/ADR will be calculated according to the preferred terms. Also, the incidence rate will be estimated.

† Subject excluded from safety per protocol set: Except for subjects who didn’t receive study vaccination and follow-up failure.

	CONFIDENTIAL :	Last Update Date
	THIS DOCUMENT AND INFORMATION CONTAINED HEREIN IS PROPRIETARY TO COMPANY AND IS NOT TO BE DISCLOSED WITHOUT THE WRITTEN PERMISSION OF COMPANY.	22-NOV-2013
STATISTICAL ANALYSIS PLAN(V2.0)		

7. List of Table and Data Listings

7.1 Distribution of Subjects

- Number of subjects contracted to the study: The number of subjects are to be collected(under contract) as contracted by the investigator
- Number of retrieving completed CRFs: Total number of subjects whose completed CRFs
- Number of safety assessment population: Number of safety assessment population among total number

